2.2.2 Secondary Endpoints

- 6 Month maintenance treatment completion as defined as completion of at least 2 of 3 maintenance treatments within a 5-week period without unacceptable toxicities or disease progression. Disease status will be evaluated based on cystoscopy and urine cytology prior to maintenance therapy.

Patients with persistent or recurrent high-grade disease at 6 Month cystoscopy will be taken off treatment. Low-grade recurrence will be tolerated without treatment interruption.

- 3-month and 6-month complete response (CR) based on negative cystoscopy and urine cytology.
- Recurrence free survival (RFS) at 6 and 12 months, defined as proportion of patients who are alive and free of persistent or recurrent NMIBC based on cystoscopy, cytology and/or biopsy.
- Progression-free survival (PFS) at 6 and 12 months, as defined by time from day of first treatment to first progression to higher grade or stage, including muscle-invasive disease or death from any cause
- Cystectomy-free survival (CFS), defined as time from study initiation to cystectomy or death
- Overall survival, defined as time from day of first treatment to death from any cause

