8.2 Efficacy Evaluation

Cystoscopy and urine cytology will be obtained at screening and at Month 3, 6, 9, and 12. Only frankly malignant cytology will be considered positive and used to determine the need for bladder biopsy and further evaluation. Three-month complete response (CR) rate, 6-month CR rate, recurrence free survival (RFS), cystectomy-free survival (C

FS), and overall survival will be evaluated as the following.

Time to High-Grade Recurrence (TTHGR) is defined as time from date of first treatment to first high-grade recurrence. Patients without a recurrence will be censored at their last cystoscopy date. Those who die without a recurrence are also counted as a recurrence and high-grade recurrence at time of death.

Time to Recurrence (TTR) is identical to TTHGR with the addition that failure with any-grade bladder cancer is considered an event.

Progression-free survival (PFS) is defined as time from date of first treatment to first evidence of muscle invasive bladder cancer, metastatic disease, or death due to any cause. Those without an event are censored at their last valid tumor assessment, or at the last tumor assessment before patient start of the new therapy if a patient has started new anti-cancer therapy.

Complete Response: For the subset of patients with CIS (with or without concomitant Ta or T1 disease) at study entry, a 6-month biopsy is required. A negative biopsy at 6 months will provide evidence of complete response. A +/- 10 day window will be allowed around the disease assessment time point. Patients receiving a second induction will not be required to undergo 6-month biopsy

Duration of Complete Response: For the subset of patients with CIS (with or without concomitant Ta or T1 disease) at study entry who achieve a CR, duration is defined as time from first documentation of CR to time of first high grade recurrence. Patients who remain CR at end of study (EOS) are censored at their last cystoscopy date.

Overall survival (OS) is defined as the duration from the first dose date of the study drug until death due to any cause. Patients who are still alive at EOS are censored on the date they will be last known to be alive. An exploratory analysis to determine OS at EOS will be estimated by the Kaplan-Meier method.

Patient Reported Outcomes:

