- e. Overall survival (OS) is defined as time in months from first dose of the drug to the date of death. Patients who are still alive at EOS are censored on the date they were last known to be alive. Survival curve for OS will be generated using the Kaplan-Meier method. Median OS with 95% CI will be computed. If overall survival cannot be calculated due to no patient deaths, it will not be reported.
- f. Recurrence free survival (RFS) at 6 and 12 months, defined as proportion of patients who are alive and free of persistent or recurrent NMIBC based on cystoscopy, cytology and/or biopsy. Survival curve for RFS will be generated using the Kaplan-Meier method. Median PFS with 95% CI will be computed. Patients without a recurrence will be censored at their last cystoscopy date.
- g. Cystectomy-free survival (CFS), defined as time from study initiation to cystectomy or death. Survival curve for CFS will be generated using the Kaplan-Meier method. Median PFS with 95% CI will be computed. If CFS cannot be calculated due to not enough patients undergoing cystectomy, it will not be reported.

9. Safety Analyses

a. Adverse Events

- i. Severity of AEs will be graded according to the CTCAE Version 5.0. Adverse events not included in the CTCAE, Version 5.0 must be graded as follows: Mild, Moderate, Severe, Life-threatening, and Fatal according to the following definitions:
 1. Mild: The AE is noticeable to the patient but does not interfere with routine activity.
 2. Moderate: The AE interferes with routine activity but responds to symptomatic therapy or rest.
 3. Severe: The AE significantly limits the patient's ability to perform routine activities despite symptomatic therapy.
 4. Life-threatening: The AE places the patient at risk of death at the time of the event.
 5. Fatal: The AE results in the death of the patient.
- ii. Frequency and severity of adverse events will be tabulated by body system, type and maximum grade. Serious adverse events will be listed.

b. Laboratory Abnormalities

- i. An abnormal laboratory value that is not already associated with an AE is to be recorded as an AE only if any one of the following criteria is met:
 1. an action on the study drug is made as a result of the abnormality
 2. intervention for management of the abnormality is required
 3. at the discretion of the investigator should the abnormality be deemed clinically significant

10. Handling of Missing Data

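### SAP 8.f contradicts itself on whether a recurrence-free death is an RFS event, and its literal event leaves out direct progression to muscle-invasive or metastatic disease

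*SAP*

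**What the plan says.** **RFS definition.** Protocol 2.2.2, SAP 2.b.iii and SAP 8.f use the same words: "Recurrence free survival (RFS) at 6 and 12 months, defined as proportion of patients who are alive and free of persistent or recurrent NMIBC", judged by cystoscopy, cytology and/or biopsy. Neither document gives a time origin for RFS.

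**RFS analysis.** SAP 8.f adds "Survival curve for RFS will be generated using the Kaplan-Meier method" and then "Patients without a recurrence will be censored at their last cystoscopy date".

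**Related endpoints in Protocol 8.2.** Time to high-grade recurrence runs from first treatment and has the same censoring sentence, but the next sentence reads "Those who die without a recurrence are also counted as a recurrence and high-grade recurrence at time of death". Time to recurrence (TTR) follows the same rules, except that "failure with any-grade bladder cancer is considered an event". PFS counts muscle-invasive disease, metastasis and death.

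**What is carried across.** Protocol 10.2 lists TTR and time to high-grade recurrence for Kaplan-Meier analysis but not RFS. SAP section 8 plans a Kaplan-Meier curve for RFS and does not mention the other two. In SAP 8.d, PFS censoring is limited to patients who neither died nor progressed; 8.f has no such limit.

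**CFS and labels.** Both documents have "Cystectomy-free survival (CFS), defined as time from study initiation to cystectomy or death", whereas PFS and OS start at first treatment or first dose. SAP 8.f and 8.g, on RFS and CFS, each say "Median PFS with 95% CI will be computed".

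**The concern.** Under the definition in 8.f, death is a failure. Under its censoring sentence, a patient who dies without a recorded recurrence is one without a recurrence, and so is censored at the last cystoscopy. Both instructions cannot be followed for the same patient.

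The event is also tied to non-muscle-invasive disease. A patient whose first failure is muscle-invasive or metastatic disease is, on the literal words, alive and free of persistent or recurrent NMIBC, and could be scored as recurrence-free.

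The stake is the RFS figure itself. Recurrence-free survival is a named secondary objective. Within the SAP it is the only recurrence endpoint timed from the start of treatment, because TTR was not carried over. Either reading that leaves an event out makes RFS look better, and a single-arm study has no comparator in which the same omission could offset it.

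**Working it through.** **The plan's own figure.** No figure is stated for RFS. The only related one is the lower Wilson 95% limit of 37.6% for a 60% completion rate in 18 patients (Protocol 10.1; SAP 3.b). With p = 0.60, n = 18, z = 1.96:

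- centre = (p + z²/2n) / (1 + z²/n) = (0.60 + 0.1067) / 1.2134 = 0.5824
- half-width = z·√(p(1−p)/n + z²/4n²) / (1 + z²/n) = 1.96 × √(0.01333 + 0.00296) / 1.2134 = 0.2062
- limits = 37.6% to 78.9%

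The figure reproduces. The RFS point does not depend on it.

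**The texts side by side.**

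| Patient's first failure | RFS definition, SAP 8.f | Censoring sentence, SAP 8.f | TTR, Protocol 8.2 |
|---|---|---|---|
| NMIBC recurrence | failure | event | event |
| Death without recurrence | failure (not alive) | censored | event |
| Direct muscle-invasive or metastatic disease | not named | depends on whether it is called a recurrence | event (bladder cancer of any grade, not limited to NMIBC) |

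**Size for 18 patients.** From the documents: n = 18 and cystoscopy every 3 months. Assumed for illustration: NMIBC recurrence in 4, 2, 1 and 1 patients at months 3, 6, 9 and 12; m direct progressions to muscle-invasive disease at month 6; d deaths without recurrence at month 8, last cystoscopy at month 6. The Kaplan-Meier estimate is the product of (1 − events / at risk) over event times.

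Worked case, m = 0 and d = 1:

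- death counted: (14/18)(12/14)(11/12)(10/11)(9/10) = 9/18 = 50.0%
- death censored at month 6: (14/18)(12/14)(10/11)(9/10) = 54.5%
- difference: 4.5 points

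Worked case, m = 1 and d = 0:

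- progression counted: (14/18)(11/14)(10/11)(9/10) = 9/18 = 50.0%
- progression scored as still free: (14/18)(12/14)(11/12)(10/11) = 10/18 = 55.6%
- difference: 1/18 = 5.6 points (4.5 points if this patient is censored at month 6 instead)

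| m | d | All counted | Literal: progression free, death censored | If alive governs: death counted, progression free |
|---|---|---|---|---|
| 0 | 0 | 55.6% | 55.6% | 55.6% |
| 0 | 1 | 50.0% | 54.5% | 50.0% |
| 1 | 0 | 50.0% | 55.6% | 55.6% |
| 1 | 1 | 44.4% | 54.5% | 50.0% |
| 2 | 1 | 38.9% | 54.5% | 50.0% |
| 3 | 2 | 27.8% | 53.3% | 44.4% |

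The gap is zero with no such events and grows by roughly 5 points for each one left out.

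**The case against.** The strongest reply is that the definition controls. It requires the patient to be alive, so the censoring sentence can be read as covering survivors only, and deaths then add no error. An invasive tumour found at cystoscopy or biopsy would naturally be called a recurrence. Invasive progression, metastasis and death are all PFS events, death is also an OS event, and the Protocol still plans TTR. RFS is descriptive, has no hypothesis or threshold, and comes from 18 patients.

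Most of this stands, and it limits the point. The documents do not plainly instruct the analyst to censor deaths; they contain two adjacent sentences that disagree. Nor are the invasive events lost to the trial. But capture in PFS does not correct the RFS number. SAP 8.d shows that the authors limited censoring to survivors when they meant to, and the natural-language reading of recurrence is one that an analyst would have to supply.

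A reader might infer more than the documents support:

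- **That CFS is misestimated.** Its origin, study initiation, is undefined. If it means first dose, the error is zero. If it means consent or screening, the shift is at most about one month (Table 7 allows 28 days). Only the trial's calendar start would matter: at one patient per month, patients 1 to 18 would gain 0 to 17 months, mean 17/2 = 8.5. Protocol 6.3.2 times 6 months from trial initiation at patient level, and Protocol 4.2 treats a patient as enrolled once treatment begins; both favour a patient-level reading. This is a term to define, not a shown bias.
- **That a proportion analysed by Kaplan-Meier is a defect.** A Kaplan-Meier estimate at 6 or 12 months is an estimated proportion.
- **That the progression rates in Protocol 1.2 (above 20% for Ta, 35% for T1) give the expected size.** They have no time frame, and the Ta figures are for patients without additional treatment.

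**Conclusion.** The point holds for the RFS event and censoring rule: SAP 8.f is internally inconsistent on recurrence-free deaths, and its literal event omits direct progression to muscle-invasive or metastatic disease. Any resulting error is upward. On the assumed pattern of visits and recurrences it is about 4.5 to 5.6 percentage points of 12-month RFS per uncounted event. It is zero if no such events occur, and confined to the invasive or metastatic gap if the word alive governs. The event counts and times are illustrative; the documents give no expected rates for this population over 12 months.

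The consequence is limited to a descriptive secondary endpoint. The primary endpoint, the dose decisions and the sample size, which was set by feasibility, are unaffected. It should be corrected before analysis, because two analysts could otherwise reach different RFS values in good faith. The CFS origin and the median labels are tidying only.

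**What to change.** In SAP 8.f, with Protocol 2.2.2 and SAP 2.b.iii brought into line:

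- Define RFS as time from first dose to the first persistent or recurrent bladder cancer of any stage, including muscle-invasive or metastatic disease, or death from any cause.
- Censor only patients who are alive and disease-free, at their last cystoscopy.
- Report Kaplan-Meier estimates with 95% confidence intervals at 6 and 12 months.

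This uses the event scope and death rule that Protocol 8.2 already applies to TTR.

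As tidying, name first dose as the CFS origin, to match PFS and OS, and change the median labels in SAP 8.f and 8.g to RFS and CFS.

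The cost is wording only, with no added visits, data or patients. RFS may come out slightly less favourable if such events occur.

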10.2 Analytic Plan

Only evaluable patients as defined in Section 8.1.1 will be included in the statistical analysis. The proportion of patients receiving a complete induction course (at least 5 of 6 treatments of each BCG and avelumab within eight weeks of starting treatment) at 3 months and at 6 months will be calculated and a 95% Wilson score confidence interval constructed for the completion rate.

The 3-month and/or 6-month complete response (CR) rates will be summarized as the proportion (and 95% CI) of patients with complete tumor response at month 3 or 6 of study treatment.

Kaplan-Meier curves will be generated for overall survival, duration of response, progression-free survival, cystectomy-free survival, time to recurrence, and time to high-grade recurrence. Median survival time and 95% confidence intervals will be calculated. The EORTC QLQ-C30 questionnaire functional scales, symptom scales, and global health and quality of life scale will be summarized.

Frequency and severity of adverse events will be tabulated by body system, type and maximum grade. Serious adverse events will be listed.

Interim analysis

An interim safety analysis will be conducted when 3~6 patients have received ≥ 5 doses of BCG treatment in dose level 1. If the combination therapy in dose level 1 is not tolerated (2 or more patients experience a DLT), dose level -1 will be evaluated in additional 3~6 eligible patients. The decision rule is fully described in Section 5.2 Overall Study Design.

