2. Endpoints

a. Primary Endpoint

- i. Completion of induction therapy with combined BCG + avelumab as defined as freedom from dose-limiting toxicity (DLT) (Section 5.2.1) preventing completion of at least 5 of 6 treatments of BCG + avelumab within 8 weeks.

b. Secondary Endpoint

- i. 6 Month maintenance treatment completion as defined as completion of at least 2 of 3 maintenance treatments within a 5 week period without DLT or disease progression. Disease status will be evaluated based on cystoscopy and urine cytology prior to maintenance therapy. Patients with persistent or recurrent high-grade disease at 6 Month cystoscopy will be taken off treatment. Low-grade recurrence will be tolerated without treatment interruption.
- ii. 3-month and 6-month complete response (CR) based on negative cystoscopy and urine cytology.
- iii. Recurrence free survival (RFS) at 6 and 12 months, defined as proportion of patients who are alive and free of persistent or recurrent NMIBC based on cystoscopy, cytology and/or biopsy.
- iv. Progression-free survival (PFS) at 6 and 12 months, as defined by time from day of first treatment to first progression to higher grade or stage, including muscle-invasive disease or death from any cause
- v. Cystectomy-free survival (CFS), defined as time from study initiation to cystectomy or death
- vi. Overall survival, defined as time from day of first treatment to death from any cause

c. Exploratory Endpoint

- i. To obtain preliminary data of potential biomarkers that would associate with tumor response from the combination of avelumab and intravesical BCG.
- ii. Avelumab combined with intravesical BCG will improve quality of life in patients with NMIBC.

3. Design information

a. General statistical considerations

- i. This is a single arm, phase Ib study. A total of 18 evaluable patients will be enrolled at the Stephenson Cancer Center. More than 40 patients with bladder cancer initiate intravesical BCG treatment in our Urologic Oncology clinic each year, including approximately 40% patients with BCG-treated but unresponsive NMIBC (persistent or recurrent) who are hopefully eligible for the proposed study. Based on our prior experience with a similar patient population, we anticipate enrollment of 1 patient per month.

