5. The following may be considered as exceptions to DLTs: 1.
- a. Grade 3 nausea, vomiting, or diarrhea and Grade 4 vomiting or diarrhea in the absence of maximal medical therapy that resolves in 72 hours.
 - b. Grade 3 fatigue lasting < 5 days.
 - c. Grade 3 hypertension that can be controlled with medical therapy.
 - d. An increase of indirect (unconjugated) bilirubin indicative of Gilbert's syndrome.
 - e. Serum lipase and/or serum amylase CTCAE Grade 3 ≤ 7 consecutive days without clinical signs or symptoms of pancreatitis.

ii. **Definition of DLT Evaluable Population**

1. Patients enrolled in safety lead-in cohort who receive at least 4 doses and complete the DLT observation period (the first 42 days of induction treatment), unless the patient discontinued the study treatment due to a DLT.

8. Antitumor Evaluation

- a. The proportion of patients receiving a complete induction course (at least 5 of 6 treatments of BCG + avelumab within eight weeks of starting treatment) at 3 months and at 6 months will be calculated and a 95% Wilson score confidence interval constructed for the completion rate.
- b. The 3-month and/or 6-month complete response (CR) rates will be summarized as the proportion (and 95% CI) of patients with complete tumor response at month 3 or 6 of study treatment. Patients who remain CR at end of study (EOS) are censored at their last cystoscopy date.
- c. The duration of response will be calculated as time from the date of first response (complete response (CR), partial response (PR), pathological complete response (pCR)) to the first date of non-response. Duration of response will be summarized using the Kaplan-Meier method. Median duration of response with 95% CI will be computed. Results will be presented in tabular and graphic form, as appropriate.
- d. Progression-Free Survival (PFS) at six month and twelve months is defined as the time in months from the first dose of the drug to the date of death or the first documented date of progression, whichever comes first. For patients who did not die and did not have progression, the PFS is censored at the last documented tumor assessment. Survival curve for PFS will be generated using the Kaplan-Meier method. Median PFS with 95% CI will be computed. Those without an event are censored at their last valid tumor assessment, or at the last tumor assessment before patient start of the new therapy if a patient has started new anti-cancer therapy.

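### SAP 8.f and 8.g name median PFS as the summary for RFS and CFS, and no 6- or 12-month Kaplan-Meier estimate with a confidence interval is specified for PFS or RFS

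*SAP*

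**What the plan says.** SAP 2.b lists "Progression-free survival (PFS) at 6 and 12 months" as a secondary endpoint. RFS is defined there, and again in SAP 8.f, as "Recurrence free survival (RFS) at 6 and 12 months, defined as proportion of patients who are alive and free of persistent or recurrent NMIBC". CFS is listed as a time to event with no landmark.

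The analysis text in SAP Section 8 then reads as follows.

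- PFS (8.d): "Progression-Free Survival (PFS) at six month and twelve months is defined as the time in months from the first dose", so the landmark label is attached to a time variable. The summary is "Survival curve for PFS will be generated using the Kaplan-Meier method. Median PFS with 95% CI will be computed".
- RFS (8.f): "Survival curve for RFS will be generated using the Kaplan-Meier method. Median PFS with 95% CI will be computed".
- CFS (8.g): "Survival curve for CFS will be generated using the Kaplan-Meier method. Median PFS with 95% CI will be computed". A further rule follows: "If CFS cannot be calculated due to not enough patients undergoing cystectomy, it will not be reported".
- Overall survival (8.e) uses the same template and names its own median correctly.

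Protocol 10.2 states "Kaplan-Meier curves will be generated for overall survival, duration of response, progression-free survival, cystectomy-free survival, time to recurrence, and time to high-grade recurrence" and then asks for median survival times with 95% confidence intervals. RFS is not on that list, and no landmark rate is mentioned.

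**The concern.** A SAP is the instruction from which tables are programmed, so the statistic it names should belong to the endpoint being reported. In 8.f and 8.g it does not.

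The second gap concerns content. An endpoint listed at 6 and 12 months calls for an estimate at each of those times and a statement of its precision. SAP 8.a and 8.b do this for completion and complete response, each a proportion with a 95% CI. SAP 8.d and 8.f do not. If few patients progress, the PFS result could be a median not reached, with no pre-specified number for the endpoint actually listed.

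For RFS the definition implies a proportion but does not say how to estimate it. A crude proportion and a Kaplan-Meier estimate treat a patient censored before month 6 differently, SAP Section 10 excludes imputation, and one patient in 18 is 1/18 = 5.6 percentage points.

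**Working it through.** **1. Endpoint against named statistic**

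| Endpoint | Listed as (SAP 2.b) | Curve (SAP 8) | Summary named (SAP 8) | Median from Protocol 10.2 | 6/12-month estimate with CI |
|---|---|---|---|---|---|
| PFS | at 6 and 12 months | PFS | median PFS | yes | none |
| RFS | proportion at 6 and 12 months | RFS | median PFS | no (time to recurrence is listed) | none |
| CFS | time to event | CFS | median PFS | yes | not required by the listing |
| OS | time to event | OS | median OS | yes | not required by the listing |

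**2. The plan's own figure.** No expected rate or precision is stated for PFS, RFS or CFS. The only precision figure is the Wilson lower limit for a 60% completion rate with n = 18 (Protocol 10.1, SAP 3.b). With z = 1.96:

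- centre = (p + z²/2n)/(1 + z²/n) = (0.60 + 0.1067)/1.2134 = 0.5824
- half-width = z·√(p(1−p)/n + z²/4n²)/(1 + z²/n) = 1.96·√(0.01333 + 0.00296)/1.2134 = 0.2062
- interval = 37.6% to 78.9%, which matches the stated 37.6%.

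**3. Can a median be reached?** With n = 18 and no censoring, the Kaplan-Meier curve falls to 0.5 at the 9th event, so P(median reached) = P(Binomial(18, q) ≥ 9), where q is the assumed proportion with an event by the end of follow-up. Values of q are borrowed from Protocol 1.2 for illustration only: progression in more than 20% (Ta, no additional treatment), 35% (T1) and up to 50% (after a third BCG cycle); recurrence in more than 60% (Ta) and more than 75% (T1).

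**4. Can its upper 95% limit be reached?** The upper limit of the median is finite only if the upper limit of the survival estimate falls below 0.5.

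- 12 events: S = 0.333, SE = √(0.333·0.667/18) = 0.111, upper limit 0.333 + 1.96·0.111 = 0.551 (log-log 0.545). Not below 0.5.
- 13 events: S = 0.278, SE = 0.106, upper limit 0.485 (log-log 0.489). Below 0.5.

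About 13 events are therefore needed.

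| Assumed q | P(≥ 9 events): median reached | P(≥ 13 events): finite upper limit |
|---|---|---|
| 0.20 | 0.4% | 0.0% |
| 0.35 | 13.9% | 0.1% |
| 0.50 | 59.3% | 4.8% |
| 0.60 | 86.5% | 20.9% |
| 0.75 | 99.5% | 71.8% |

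The first three rows bracket the progression figures and the last two the recurrence figures.

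**5. What a landmark estimate would give.** With no censoring, Wilson 95% intervals for n = 18 are 57.1% to 92.3% for 80% event-free, 42.2% to 82.5% for 65%, and 29.0% to 71.0% for 50%. These are wide, but both limits exist in each case.

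**The case against.** The other side has four fair arguments.

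*The label is a slip.* The sentence before it draws the correct curve each time, 8.e shows the intended template, and Protocol 10.2 already asks for a median for CFS. A reader might infer that the RFS and CFS sections would end up carrying the PFS figure. The documents do not support that as a likely outcome, because an analyst would have to draw one curve and print another endpoint's median beside it. Protocol 10.2 also gives a median for time to recurrence, which Protocol 8.2 defines with deaths counted as events, so a close relative of median RFS is planned. This stands as mitigation. But no document equates the two, time to recurrence does not appear in SAP Section 8, and the text still needs correcting.

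*The 6- and 12-month values can be read off the curve.* This is true, so it would be wrong to say that 8.d yields only a median. What is missing is a named estimate with an interval.

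*The PFS median is not shown to be out of reach.* A reader might infer from the 20% and 35% figures that it will almost never be reached. That is not established. The background rates carry no time horizon and come from other settings. At the 50% figure in the same section the chance is 59%. Deaths count as PFS events, and SAP 2.b also counts a rise in grade or stage, so progression rates alone may understate events. With censoring, a median can be reached on fewer than nine events.

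*CFS is not a landmark endpoint.* A reader might want 6- and 12-month CFS, or a particular interval method, treated as required. Neither document defines CFS at fixed times, so both are preferences.

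**Conclusion.** The point holds as a correction to the SAP text. The wrong median is named in 8.f and 8.g, an evident copy error that Protocol 10.2 offsets for CFS but not for RFS. PFS and RFS are listed at 6 and 12 months without a named Kaplan-Meier estimate and interval at those times.

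The consequence is that the named PFS summary may be uninformative. Across assumed event proportions of 20% to 50%, the median is reached with probability 0.4% to 59%, and its upper limit is finite in at most about 5% of cases. This rests on 18 patients, no censoring and borrowed background rates, since the plan states no PFS rate. It shows a range and does not predict this trial.

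Severity is minor. These are descriptive secondary endpoints in a single-arm study sized on feasibility, and neither the primary endpoint nor the sample size depends on them.

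**What to change.** - SAP 8.f: replace median PFS by median RFS.
- SAP 8.g: replace median PFS by median CFS.
- SAP 8.d and 8.f: specify Kaplan-Meier estimates at 6 and 12 months with 95% CI as the summary of the listed endpoint, with the median and its CI reported if reached. State the interval method.
- SAP 8.d: define PFS as a time to event and separate that definition from the 6- and 12-month estimates taken from its curve.
- Optional: add landmark CFS. If few patients have a cystectomy, it would still report that result where 8.g would leave it out.

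The cost is a few words of SAP text and a few extra output columns. No additional data are needed and nothing changes for patients.
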